RSV is a major cause of respiratory infection in all ages, which can result in severe illness in both infants and older adults.¹⁻⁴ Like influenza, RSV infection follows a seasonal pattern, causing yearly wintertime epidemics in temperate climates. Although most well recognized as a pediatric pathogen, RSV was first acknowledged as a serious threat to adults when outbreaks of acute respiratory infection (ARI) with high pneumonia and mortality rates were reported in nursing homes settings in the 1980s.^{5,6} Since the initial reports, prospective studies demonstrate infection rates in LTCF ranging from 1-12%.⁷⁻¹⁰ RSV infection is particularly problematic for very elderly adults and those with underlying medical conditions, particularly heart and lung disease.^{1,11-13} RSV not only causes respiratory tract infection but can also trigger exacerbations of underlying comorbid conditions such as COPD and CHF.¹⁴ RSV infection has been associated with up to 22% of acute COPD exacerbations in prospective cohort studies and 11% of wintertime hospitalizations for COPD exacerbations.^{1,15}

Current epidemiology shows that RSV is responsible for approximately 100,000-177,000 hospitalizations and 9,000-14,000 deaths annually in US adults 65 years of age and older.^{4,16,17} Morbidity is significant among adults hospitalized with RSV disease, with 18% requiring intensive care, 31% needing home health services at discharge, and 26% dying within 1 year of hospitalization. In some studies, the risk of poor outcomes and death is higher among patients hospitalized for RSV compared to influenza.^{13,18} In addition to the acute morbidity, longer term functional loss has been demonstrated following RSV hospitalization and the group most severely affected are residents of LTCFs.¹⁹ The overall burden of adult RSV disease is likely underestimated since testing for RSV is less common in older adults than in children and RSV is more difficult to detect due to low levels of virus in the upper airways.^{20,21}

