This is an open label non-inferiority study where all participants will receive either the licensed Pfizer RSV Vaccine (ABRYSVO) or the GSK RSV Vaccine (AREXVY) as part of Standard of Care (SOC) and immune responses will be compared between adults living in the community and adults living in LTCF. The vaccines available at the participating LTCF as part of SOC will direct what product is administered at the individual LTCF and the community cohort will be matched for similar proportions of ABRYSVO and AREXVY.

Primary Objectives:

Demonstrate that the peak immune response at 1 month post vaccination of adults 60 years and older residing in LTCF is non-inferior to community-dwelling adults 60 years and older as measured by:

- Serum neutralizing antibody against RSV A & B

Secondary Objectives:

Demonstrate that the peak immune response at 1-month post vaccination of adults 60 years and older residing in LTCF is non-inferior to community-dwelling adults 60 years and older as measured by:

- Serum binding antibody to RSV prefusion F protein against RSV A & B

Study Period and Sites:

The study will be conducted at the University of Rochester Medical Center (URMC) in collaboration with 2 local LTCFs and include the Highlands at Brighton and St. Ann's Home. These LTCFs are located geographically close to URMC and have expressed a high interest in participating in this study. The study period will be from November 2023 to April 2024. There will be 1 month of direct participant involvement and 6 months for completion of the immune assays and data analysis.

Participant Recruitment:

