- Obtain and record the participant's demography (including complete date of birth, sex, race, racial designation, and ethnicity)
- Obtain and record medical history
- Obtain and record details of any non-study vaccinations, and prohibited concomitant medications and treatments
- Perform a clinical assessment including vital signs (Blood pressure, heart rate and oxygen saturation) and symptom-targeted physical exam
**Note: Height and weight will be recorded as by participant report or medical record in LTCF.*
- Collect 10 cc of serum
- Confirm contact and alternate contact information with participant and LTCF staff
- Schedule visit 2.

Visit 1 (Standard of Care) [Vaccination: For LTCF this will be performed by LTCF staff per their facility protocol and for Community Cohort this will be performed in the clinic]

- Perform a clinical assessment including vital signs (Blood pressure, heart rate and temperature) and symptom-targeted physical exam as dictated by location of vaccination standard procedures.
- Vaccinate with ABRYSVO or AREXVY and in non-dominant arm and document product, time and location.
- 15 minutes of observation in the clinic, in LTCF standard practice will be followed

If a person has an intercurrent RSV infection and is not vaccinated as part of SOC, visit 2 will be scheduled 28-42 days after infection was documented.

Visit 2 (Research Procedures) [1-month]

- Verbally confirm the participant wishes to continue in the study
- Obtain and record any new medical history
- Inquire about any respiratory illnesses and record results any viral testing performed.
- Collect information on AEs, SAEs related to study procedures
- Obtain and record details of any non-study vaccinations, and prohibited concomitant medications and treatments
- Perform a symptom-targeted clinical assessment and physical exam
- Collect 10 cc of serum.

Individuals who do not meet the criteria for participation in the study (screen failure) can be rescreened if the exclusionary condition is considered to be temporary in nature by the investigator.

Only the following information will be collected on screen failures: demographics (age, screen number, sex, ethnicity, and race) and reason for ineligibility. Participants who are found to be ineligible will be told the reason for ineligibility.

LABORATORY METHODS:

RSV PCR will be performed as standard of care in the LTCF.

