Enzyme Immunoassay (EIA): Serum IgG titers to RSV F (prefusion) protein of group A and B RSV will be determined by enzyme immunoassay using established methods.²⁸ Briefly, purified RSV proteins are coated to 96-well EIA plates to which serum 2-fold dilutions are added in duplicate. Bound antibody is detected with alkaline phosphatase-conjugated goat anti-human IgG antibody and substrate.

Microneutralization Assay (MNA): Serum neutralizing titers will be performed using an established microneutralization method for RSV A and B strains.²⁸ Briefly, 2-fold serum dilutions are incubated with 75 plaque forming units of RSV for 30 min at room temperature followed by the addition of 10⁴ HEp-2cells in 96-well culture plates. After 3 days, the quantity of RSV antigen is determined by enzyme immunoassay using a monoclonal antibody to the RSV F protein. The neutralization titer is defined as the serum dilution that results in a 50% reduction in color development.

ANALYTICAL AND STATISTICAL METHODS

The primary immunogenicity analysis will include persons vaccinated but without documented RSV infection (PCR or G ELISA). The immune response to infection alone or combined infection and vaccination will be analyzed descriptively and separate from the primary analysis. This study is designed to demonstrate non-inferiority to within a 1.5-fold difference in the 1-month titer level, adjusting for baseline titer level. Since the distribution of titer levels is strongly positively skewed, and we are interested in relative changes, all titer levels

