will be log transformed to help symmetrize the distribution while simultaneously stabilizing the variance. Exponentiating arithmetic mean log(titer), and their differences, thus results in geometric mean titer levels, and relative changes therein, which are the desired metrics. A linear model will be used to model log (1-month titer) as a function of an indicator for population, adjusted for continuous log (baseline titer). This model is equivalent to modeling log (relative change in titer), 1-month vs baseline, as a function of an indicator for population, adjusted for continuous log (baseline titer). The adjustment for log (baseline titer) improves statistical efficiency compared with using a 2-sample t-test to compare either (a) log (relative change in titer) or (b) log (1-month titer) by population, while obviating the choice between them. The focal parameter is the regression coefficient on population, whose antilog represents the ratio (test population vs reference population) of the adjusted geometric mean titer level (and, equivalently, the ratio of the adjusted relative geometric mean 1-month change in titer level). If the 1-sided 95% lower bound for this ratio exceeds 2/3, indicating with 95% confidence that the geometric mean titer level for the test population is at least 2/3 as high as that of the reference population (i.e. that the geometric mean titer level for the reference population is at most 1.5 times that of the test population), then we will conclude non-inferiority of the test population relative to the reference population.

Power and Sample Size Considerations:

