Based on data from 52 participants in a prior study of the Pfizer RSV vaccine, the geometric mean titer level was estimated to be 2218 (95% CI: 1822-2699) at baseline, and 22,510 (17,003-29,799) at 1-month, corresponding with a relative change of 10.15-fold (95% CI: 7.39-13.95). From this data we estimate the Standard Deviation (SD) of log(titer) to be 0.71 at baseline and 1.01 at 1-month, while the SD of the 1-month change in log(titer) is 1.14 –larger than SD (log (1-month titer)), indicating that a 2-sample t-test of the change in log(titer) would be less efficient than a t-test of the 1-month log(titer). Since we plan to adjust for baseline log(titer), our residual SD $< \min(\text{SD}(\log(1\text{-month titer})), \text{SD}(\log(\text{relative change in titer}))) = \min(1.01, 1.14) = 1.01$. But not much less, since the prior data suggests the correlation between baseline and 1-month log(titer) is very weak ($r=0.14$), with log (baseline titer) explaining only 2% of the variability in log (1-month titer). In particular, we estimate residual SD = 1, suggesting that a 2-sample t-test of log (1-month titer) would be nearly as efficient as our linear model-based test adjusting for log (baseline titer). Given this estimate of variability (SD=1), a sample size of 76, 89, or 105 per group provides 80%, 85%, or 90% power to demonstrate non-inferiority to within a relative non-inferiority margin of 1.5-fold using a 1-sided 0.05 level linear model-based t-test comparing log (1-month titer) by population, adjusted for log (baseline titer). We have chosen a sample size of 76 in each group which will provide 80% power to demonstrate non-inferiority.

POTENTIAL RISKS AND BENEFITS

This study may be associated with risk due to sample collection or loss of privacy.

Sample Collection:

- **Blood draws:** A blood draw may cause faintness, inflammation of the vein, pain, bruising, or bleeding at the site of the puncture. There is also a slight chance of infection.

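### Vaccine product is the only factor on which the community cohort is matched, yet the primary model omits it; a one-df product term would reduce a residual and probably small risk

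*Combined protocol and SAP*

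**What the plan says.** Study Design and Objectives (combined protocol and SAP): facility supply "will direct what product is administered at the individual LTCF", and "the community cohort will be matched for similar proportions of ABRYSVO and AREXVY". No tolerance is given for similarity, and the section does not say whether the enrolled or the analysed participants are to be matched. No other matching factor is named.

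Study Procedures, Visit 1: staff are to "document product, time and location", so product will be known for every vaccinated participant. Vaccination of the other group is under the study team's eye: "for Community Cohort this will be performed in the clinic".

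Analytical and Statistical Methods: the model will "model log (1-month titer) as a function of an indicator for population, adjusted for continuous log (baseline titer"). Product appears there neither as a covariate nor as a stratum, sensitivity analysis or subgroup. The analysis set is defined after exclusions: "The primary immunogenicity analysis will include persons vaccinated but without documented RSV infection (PCR or G ELISA").

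Power and Sample Size Considerations: the variability estimate is "Based on data from 52 participants in a prior study of the Pfizer RSV vaccine", that is, from one product.

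**The concern.** A factor important enough to match on is normally carried into the model. Here the match is on group proportions only, to an unstated tolerance, and exclusions come afterwards. If the two vaccines give different titers and the product shares differ between the cohorts in the analysed set, part of the product difference is read as a population difference.

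Non-inferiority rests on one lower bound compared with 2/3. A mismatch in favour of LTCF residents raises the chance of a false non-inferiority conclusion; one against them lowers power. Even with equal shares, between-product variation left in the residual costs some power. The planned analysis would not show which of these situations applies.

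**Working it through.** **Inputs from the documents.** 76 per group; one-sided 5% level; margin ln(1.5) = 0.4055; residual SD 1; baseline SD 0.71; baseline to 1-month correlation 0.14 (Analytical and Statistical Methods; Power and Sample Size Considerations).

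**Assumed, because the documents give no values.** Product geometric mean titer ratio g = 1.25, 1.5 or 2 (2 is extreme); about a 50:50 split; the same residual SD of 1 within each product.

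**The plan's own figure.** SE = sqrt(2/76) = 0.1622. Non-centrality = 0.4055/0.1622 = 2.50. With a critical t of 1.655 on 149 df, the non-central t gives power 80.0%. The same calculation gives 89 and 105 per group for 85% and 90%. All three stated sizes reproduce.

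**Bias.** Log bias = (difference in product share in the analysed set) × ln(g). It is zero at an exact match.
- Two persons, 39 vs 37 of 76: 2/76 = 0.026; the ratio shifts by 0.6/1.1/1.8%.
- Eight persons, 42 vs 34 of 76: 8/76 = 0.105; log bias 0.023/0.043/0.073; the ratio shifts by 2.4/4.4/7.6%.

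**Exact match, no product term.** With balanced counts, product adds nothing to the variance of the population contrast, but it does enter the residual variance that the trial estimates: about 1 + 0.25 × (ln g)² × 152/149. The estimated SD is then 1.006/1.021/1.059 times too large for this contrast. Type I error is P(T > 1.655 × that factor), about 4.9/4.7/4.1%, so the test is slightly conservative.

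**Operating characteristics.** The planned model was simulated with fixed product counts, with and without a product term (200,000 trials per setting; Monte Carlo error about 0.1 point). Values are for g = 1.25/1.5/2.

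| Product counts, LTCF vs community | Type I error, mismatch favours LTCF, no term | Power, mismatch against LTCF, no term | With term |
|---|---|---|---|
| 38 vs 38 (exact) | about 5/4.7/4% | 79.7/78.9/76.9% | 5.0%; 79.8% |
| 39 vs 37 | 5.3/5.4/5.2% | 78.6/77.0/73.4% | 5.0%; 79.8% |
| 42 vs 34 | 6.5/7.8/9.9% | 75.2/70.8/61.4% | 5.0%; 79.5% |

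If the direction of mismatch is arbitrary, the average type I error without the term is 4.9/4.8/4.2% (two persons) and 5.0/5.2/5.7% (eight persons).

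**Can infection exclusions break the match?** Only to a limited extent. Four LTCF residents lost, all on one product and none in the community: 38/72 − 0.5 = 2.8 points, which gives about the same type I error as the two-person row. Background and Rationale says "prospective studies demonstrate infection rates in LTCF ranging from 1-12"%, without a time period. At the top of that range, 12% of 76 is about 9: 38/67 − 0.5 = 6.7 points, with type I error 5.8/6.4/7.1% or power 74.5/71.1/65.0%. Part of that power loss is the smaller sample: with the term, power is still only about 77.3%.

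**Cost of the term.** Residual df go from 149 to 148; power stays at 80.0% with equal shares. With a share difference d the variance inflation is 1/(1 − d²): 1.010 at d = 0.10 (power 79.7%) and 1.042 at d = 0.20 (78.6%).

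**The case against.** The strongest reply is that the design already deals with this. The community cohort is matched on product and vaccinated in the research clinic, so the mix can be watched and steered during enrolment. At a plausible two-person mismatch, type I error moves by less than half a point even at g = 2. The large figures combine an extreme product difference with a mismatch that hardly counts as similar proportions. The exclusion scenario at 9 residents is also stacked: top of the range, one product only, none in the community, and a 1-month window. The documents give no evidence that the products differ in titer, or that both will be used. All of this stands, and it is why the point is minor. It does not remove the case for the term, because some power is recovered even at an exact match whenever the products differ.

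Three stronger readings are tempting and not supported:
- A reader might infer that the comparison is biased or the false non-inferiority rate inflated. Neither the product difference nor any mismatch is given, the bias is zero at an exact match, and the direction is unknown.
- A reader might infer that the test is conservative at an exact match because the planning SD came from a single-product study. The planning SD does not enter the test. The conservatism comes from product variation in the trial's own residual variance. What the single-product SD does mean is separate: the stated 80% power makes no allowance for between-product variation.
- A reader might infer that a product term removes the risk outright. Facility supply sets the product, and there are two facilities, so product may coincide with facility within the LTCF group. Full removal needs the same product effect in both populations and no facility effect.

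**Conclusion.** The omission is a matter of record; its effect is conditional and probably small. This is a free improvement, not an error in the sample size or the design. Under the assumed g of 1.25 to 2 and a 50:50 split, leaving product out costs from about 0.1 to about 3 points of power at an exact match. At a two-person mismatch it adds at most about 0.4 points of type I error, or costs about 1 to 6 points of power, depending on direction. Distortion to about 10% type I error or 61% power needs an eight-person mismatch and g = 2 together. Confidence is high that the term is missing, and low to moderate on impact, because both the product difference and the mismatch are assumed. If one product is used throughout, the point is void.

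**What to change.** When both products are used:
- Pre-specify the recorded product indicator (ABRYSVO or AREXVY) in the linear models for the primary and secondary endpoints, before titers are seen.
- Report the product split by population in the analysed set, after infection exclusions.
- Give LTCF/community ratios by product descriptively only. With about 38 per group per product, the one-sided 95% lower bound lies exp(1.666 × sqrt(2/38)) = 1.47-fold below the estimate, too wide to test the margin.
- State the limit of the adjustment. If the within-product population ratios differ 1.25-fold or 1.5-fold, then at a 10-point mismatch the adjusted coefficient departs from the average weighted by the LTCF mix by about 1.1% or 2.0% (0.05 × ln 1.25 = 0.011; 0.05 × ln 1.5 = 0.020). A facility effect could not be separated from product if each facility stocks one product.

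Cost: one degree of freedom and no new data, visits or participants. The loss of power is below 0.1 points at an exact match, about 0.4 points at a 10-point imbalance and about 1.4 points at 20 points.

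### Does the non-inferiority conclusion overreach because the sentence interpreting the bound leaves out the word adjusted?

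*Combined protocol and SAP*

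**What the plan says.** All the relevant text is in the combined protocol and SAP.

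- **Analytical and Statistical Methods, design statement.** The study is "designed to demonstrate non-inferiority to within a 1.5-fold difference in the 1-month titer level, adjusting for baseline titer level".
- **Same section, model.** Log 1-month titer is regressed on a population indicator and log baseline titer. The antilog of the population coefficient is "the ratio (test population vs reference population) of the adjusted geometric mean titer level".
- **Same section, decision rule.** "If the 1-sided 95% lower bound for this ratio exceeds 2/3", non-inferiority is concluded. The explanatory clause attached to the rule, "indicating with 95% confidence that the geometric mean titer level for the test population is at least 2/3 as high", and the parenthesis after it, speak of geometric mean titer levels without the word adjusted.
- **Same section, rationale.** "The adjustment for log (baseline titer) improves statistical efficiency compared with using a 2-sample t-test" of either the change in log titer or the 1-month log titer.
- **Power and Sample Size Considerations.** "the prior data suggests the correlation between baseline and 1-month log(titer) is very weak" (r = 0.14). The residual SD is taken as 1, and 76 per group gives 80% power for the baseline-adjusted test.
- **Study Design and Objectives.** Groups are defined by residence, and "the community cohort will be matched for similar proportions of ABRYSVO and AREXVY". The primary objective refers to the 1-month response and does not mention baseline.

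No unadjusted comparison of 1-month titers is listed as an analysis.

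**The concern.** In a randomised trial the adjusted and crude ratios have the same target, so leaving out the word adjusted would not matter. Here LTCF residents and community adults may differ in baseline titer, and a real difference would not shrink as the sample grows. If baseline also predicts the 1-month titer, the two ratios are different quantities. Taken literally, the interpretive clause attaches 95% confidence to the ratio of raw population GMTs, which the model does not test. The study is meant to inform vaccination of LTCF residents, so a reader could carry away a statement about actual titer levels that the test had not established, with no planned crude ratio to compare against.

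A second, smaller point is that the plan says without condition that adjustment improves efficiency. When group baselines differ, adjustment also carries a variance cost.

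**Working it through.** **Inputs.** From Power and Sample Size Considerations: SD of log titer 0.71 at baseline and 1.01 at 1 month, r = 0.14 from 52 participants, residual SD 1, n = 76 per group, one-sided 0.05. The margin is ln 1.5 = 0.405. Baseline gaps between the groups are assumptions.

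**1. The plan's figures reproduce.**
- SDs from the reported confidence intervals: ln(2699/1822)/(2 × 2.008) × √52 = 0.71, and ln(29799/17003)/(2 × 2.008) × √52 = 1.01.
- Residual SD: 1.01 × √(1 − 0.14²) = 1.00.
- Sample size: 2 × (1.645 + 0.842)²/0.405² = 75.2, so 76. The noncentral t power at 76 is 80.0%.

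**2. Gap between the two ratios.** The slope is 0.14 × 1.01/0.71 = 0.199. Write R0 for the LTCF/community baseline GMT ratio. Then adjusted ratio = crude ratio × R0^(−0.199).

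| LTCF baseline | Adjusted ÷ crude |
|---|---|
| 1.22-fold lower | 1.040 |
| 1.5-fold lower | 1.084 |
| 2-fold lower | 1.148 |
| 1.5-fold higher | 0.922 |

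A 2-fold gap is ln 2/0.71 = 0.98 baseline SDs, which is large.

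**3. Level of the planned test.** With the adjusted ratio set at exactly 2/3, the pass rate is 5.0% at every baseline gap examined.

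**4. The alarming figures.** Now set the *crude* ratio at 2/3. The standard error is √(2/76 + g²/(150 × 0.71²)), with g the log baseline gap. For a 1.5-fold lower LTCF baseline it is √(0.0263 + 0.0022) = 0.169. The shift is 0.199 × 0.405 = 0.081, or 0.48 standard errors. The pass rate is about 1 − Φ(1.655 − 0.48) = 12%. The full calculation and a 40,000-trial simulation agree. At 1.22-fold and 2-fold lower the rates are 8% and 19%. At 1.22-, 1.5- and 2-fold higher they are about 3%, 1.7% and 0.8%.

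**5. Power.** At a true adjusted ratio of 1, power is 80% with equal baselines, 77% at a 1.5-fold gap and 72% at a 2-fold gap.

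**6. Efficiency.** Adjustment beats the t-test of 1-month titer when 1/(1 − r²) exceeds 1 + d²/4, where d is the gap in baseline SDs. At r = 0.14, d = 2 × √0.0200 = 0.283, so the break-even gap is exp(0.283 × 0.71) = 1.22-fold. At r = 0 it is 1.0-fold. At r = 0.40, d = 2 × √0.1905 = 0.873 and it is 1.86-fold. Against the change score the break-even is d = 2 × √(1.14² − 1) = 1.09, or 2.18-fold.

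**7. Reading the text.** The rule tests "this ratio", and the only ratio defined before it is the adjusted one. The clause in question explains that bound and sets no separate criterion. It never says unadjusted or crude.

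**The case for a change.** The best case for a change has four parts.

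- **The plan's own vocabulary.** Earlier in the same paragraph, geometric mean titer levels are obtained by exponentiating mean log titers, which describes raw GMTs, and these are called the metrics of interest. With an objective that does not mention adjustment, the literal reading has some support. This stands as a reason the clause could have been tighter. It does not displace the definition of the tested parameter, which is explicit.
- **Uncertain correlation.** With 52 participants the 95% interval for r is about −0.14 to 0.40. With LTCF baseline 1.5-fold lower, the pass rate at a crude ratio of 2/3 is 1.7%, 5%, 12% and 42% at r of −0.14, 0, 0.14 and 0.40. So the ratios could diverge more than r = 0.14 suggests. But the 42% pairs the upper limit of r with an assumed gap, and it is still not an error rate of the planned test.
- **Disagreement between analyses.** At a true adjusted ratio of 1, adjusted and unadjusted bounds give different verdicts in about 3% of trials with equal baselines, 14–15% at a 1.5-fold gap and 23–25% at 2-fold. A reader would want to see both. Baseline and 1-month GMTs by group are routine reporting and supply the crude ratio. Its absence from the plan does not make the primary inference wrong. Requiring both bounds to pass would cut power from 77% to 63% with LTCF baseline 1.5-fold lower.
- **Efficiency wording.** It is true that the gain is not assured in every case. But once the two ratios differ, the methods estimate different things and their relative precision has no clear meaning. The power section already says the simple t-test would be nearly as efficient, so nothing is oversold and no decision depends on it.

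**Conclusion.** The concern does not call for a change. Followed as written, the plan gives a valid 5% test of a clearly defined parameter, with a margin and sample size that reproduce for that parameter. The missing word is a slip in an explanatory clause whose antecedent is the adjusted ratio.

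At the plan's r = 0.14, the adjusted and crude ratios differ by about 4% at an assumed 1.22-fold baseline gap, 8% at 1.5-fold and 13–15% at 2-fold, depending on direction. These figures assume a common slope in both groups and the prior study's SDs. The documents give no baseline difference between the populations. If a large gap appeared, the results should describe the finding as baseline-adjusted. The model and its defined coefficient already lead there, and baseline titers are collected for everyone. Rewriting the clause, adding a supportive crude ratio or qualifying the efficiency remark would change neither the primary result nor the rule for reaching it.

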Objectives: The primary objective of this study is to compare the neutralizing antibody response at one-month post-vaccination with a licensed RSV vaccine in adults \geq 60 years of age living in skilled nursing facilities with adults living in the community. A secondary objective will be to evaluate the binding antibody responses to RSV preF proteins at 1 month.

Study Design

The study will be conducted at URMC and 2 local LTCFs. Approximately 76 persons \geq 60 years of age who live in LTCF and an equal number of older adults living independently in the community who are planning to receive one of the licensed RSV vaccines as part of standard of care (SOC) will be recruited for participation in the study.

Study procedures: Visits will occur at the LTCF for residents of LTCF or in the research clinic for community-dwelling older adults. After informed consent by the participant or legally authorized representative (LAR), demographic and medical history will be collected and a symptom-targeted physical exam will be performed. A 10 cc blood sample will be collected prior to vaccination. Following vaccine administration, individuals will be monitored for 15 minutes for immediate adverse events. One additional visit will occur at 1 month post vaccination at which time 10 cc of blood will be collected, the participant will be interviewed and medical records reviewed. Subjects will be queried about any intervening respiratory illnesses and persons testing positive for RSV infection as part of the standard of care (SOC) after vaccination or by a non-vaccine RSV protein by ELISA and before the 1-month blood draw will not be included in the immunogenicity analysis. Serum samples will be tested for binding (RSV A and RSV B PreFusion F, Attachment (G) protein) and neutralizing antibodies to RSV A and RSV B in the URMC research laboratory.

BACKGROUND and RATIONALE

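### The primary objective rests on two neutralizing titers (RSV A and RSV B), but the decision rule covers one ratio and the 80% power covers one test on an unnamed titer.

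*Combined protocol and SAP*

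**What the plan says.** - **Objective.** Under Study Design and Objectives, the single primary objective is non-inferiority of the long-term care facility (LTCF) residents at one month, measured by "Serum neutralizing antibody against RSV A & B".
- **Assays.** Two results per serum are planned. The synopsis lists "neutralizing antibodies to RSV A and RSV B in the URMC research laboratory", and Laboratory Methods says "Serum neutralizing titers will be performed using an established microneutralization method for RSV A and B strains".
- **Decision rule.** Analytical and Statistical Methods describes one linear model with one focal coefficient. The criterion is "If the 1-sided 95% lower bound for this ratio exceeds 2/3", and the consequence is "then we will conclude non-inferiority of the test population relative to the reference population". No strain is named. The passage opens with general wording ("Since the distribution of titer levels is strongly positively skewed, and we are interested in relative changes, all titer levels" are to be log transformed), so it can be read as a template for every titer.
- **Power.** Power and Sample Size Considerations uses one titer series from 52 participants in a prior study: "the geometric mean titer level was estimated to be 2218 (95% CI: 1822-2699) at baseline", and 22,510 at one month. The strain is not given. It derives a residual SD of 1 and concludes: "We have chosen a sample size of 76 in each group which will provide 80% power to demonstrate non-inferiority".

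No section expressly says how the RSV A and RSV B results combine.

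**The concern.** Two titers feed one primary objective, so the reader needs to know what counts as success. Two routes through the text lead to different places.

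1. **Both strains must pass.** This is the ordinary sense of the objective. Error is controlled without any alpha split, but the chance of meeting the objective is lower than the power for one strain, and the plan reports only the latter.
2. **The rule is applied to each titer in turn.** Its conclusion is about the population and not about a strain, so one passing strain is enough to trigger it. This is the only route on which multiplicity raises the error above the stated 5%.

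The routes part company when one strain passes and the other does not. The study is open label, and with the rule unwritten the choice between them could be made once titers are known. The background section says the data should help support the likely benefit of vaccination in LTCF residents, so what counts as meeting the objective matters.

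**Working it through.** **Inputs from the plan:** 76 per group; margin 1.5-fold, ln 1.5 = 0.4055; one-sided alpha 0.05; residual SD 1 on the natural log scale. A true ratio of 1 is implied by the stated power but not written.

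**Inputs not in the documents, shown as ranges:** the within-person residual correlation between log A and log B titers, and the second strain's SD.

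**Step 1: the plan's SD.** The one-month interval 17,003 to 29,799 has log half-width (ln 29,799 − ln 17,003)/2 = 0.2805. Multiplying by √52 and dividing by t(0.975, 51 df) gives SD 1.01. Adjusting for baseline with r = 0.14 gives 1.01 × √(1 − 0.14²) = 1.00. This matches the plan.

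**Step 2: the plan's power for one titer.** The noncentrality is 0.4055/(1 × √(2/76)) = 2.499, with df = 2 × 76 − 3 = 149 and critical t = 1.655. The noncentral t distribution gives power 0.800. At 89 and 105 per group it gives 0.853 and 0.900. The plan's 80%, 85% and 90% are reproduced.

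**Step 3: both strains must pass.** At correlation 0 and SD 1 for both, joint power is 0.8004² = 0.641. Other values come from simulating two correlated t statistics (first-strain SD 1, true ratio 1 for both):

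| Second-strain SD | Its own power | Joint power at correlation 0 | 0.5 | 0.8 | 0.9 | 0.95 |
|---|---|---|---|---|---|---|
| 0.7 | 97% | 78% | 79% | 80% | 80% | 80% |
| 0.9 | 87% | 69% | 73% | 77% | 78% | 79% |
| 1.0 | 80% | 64% | 69% | 73% | 75% | 77% |
| 1.1 | 73% | 59% | 64% | 68% | 70% | 72% |

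One-sided error cannot exceed 0.05, because the objective is met only if each of two 0.05-level tests rejects.

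**Step 4: exactly one strain passes.** The probability is p₁ + p₂ − 2 × (joint power). At SD 1 and correlation 0 it is 2 × (0.8004 − 0.6407) = 0.319.

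| Second-strain SD | Correlation 0 | 0.5 | 0.8 | 0.9 | 0.95 |
|---|---|---|---|---|---|
| 0.7 | 22% | 19% | 18% | 17% | 17% |
| 1.0 | 32% | 23% | 14% | 10% | 7% |
| 1.1 | 36% | 26% | 17% | 12% | 10% |

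A less variable second strain largely removes the power loss of Step 3, but not the split results.

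**Step 5: either strain suffices.** With both true ratios at 2/3, the chance of at least one pass is 0.05 + 0.05 − P(both pass). At correlation 0 it is 0.10 − 0.0025 = 9.75%. From the bivariate normal at correlations 0.5, 0.8, 0.9 and 0.95 it is 8.8%, 7.5%, 6.8% and 6.3%.

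**The case against.** The strongest reply has four parts.

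- **The objective already implies the rule.** Its ordinary sense is that both strains are needed, so a split means the objective is not met. This largely stands: the rule is implied, and it would be too strong to say the plan gives no guidance. But the only written decision rule does not repeat it. On that same reading, the power section's unqualified 80% is not the power for the objective unless the second strain is clearly less variable or the titers are almost perfectly correlated.
- **The power statement is tied to a single t-test and is right for that test.** This stands, and a reader should not infer a calculation error. What is missing is the link from that test to the two-titer objective.
- **Zero correlation is extreme for two titers from the same serum by the same method.** This is fair. At correlations of 0.9 to 0.95 with equal SDs, the power loss is 3.5 to 5 points and splits fall to 7% to 10%. The documents give no correlation, so neither end of the range is established.
- **Nothing shows an intention to choose the rule late.** This is also right. The gap is an opportunity, not evidence of a plan to use it.

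A reader might also infer that a split produces two contradictory conclusions. The text does not support this: the rule says when non-inferiority is concluded and is silent otherwise. A split gives one conclusion and one absence of a conclusion.

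**Conclusion.** The concern holds and should be fixed, although it is a matter of wording. The plan does not expressly join its two primary titers to its single decision rule, and its 80% is the power for one strain.

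If both must pass, the cost is power alone: about 64% to 77% at SD 1 for both strains, and a negligible loss (78% to 80%) if the second strain's SD is 0.7. If the rule is run titer by titer with a population-level conclusion, the cost is error of about 9.8% to 6.3% at the margin. Exactly one strain passes in about 32% to 7% of trials at SD 1. These ranges assume 76 analysed per group and correlations of 0 to 0.95. The power and split figures also assume a true ratio of 1; the error figures assume that both titers are at the margin.

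A reader might infer that the type I error is inflated whatever the plan means. It is not: on the more natural reading, error stays at or below 5%.

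**What to change.** Make these changes before any titers are seen.

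1. **Analytical and Statistical Methods.** State that the model is fitted separately to the RSV A and RSV B neutralizing titers, and that the primary objective is met only if the one-sided 95% lower bounds for both adjusted ratios exceed 2/3. No alpha split is needed.
2. **Power and Sample Size Considerations.** Say that 76 per group gives 80% power per strain at a true ratio of 1 and SD 1. Add that power for both strains, with SD 1 for each, is about 64%, 69%, 73%, 75% and 77% at A-B correlations of 0, 0.5, 0.8, 0.9 and 0.95. Add that it is higher or lower if the second strain's SD is below or above 1.
3. **Planning data.** Name the strain behind 2218 and 22,510.

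If the sponsor prefers separate strain-specific primary claims, each conclusion must name its strain and no population-level claim may rest on one strain alone. The plan should then disclose that, with both titers at the margin, the chance of at least one false claim is about 6% to 10% unless alpha is adjusted.

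The cost is a few sentences. Sample size, model and margin stay as they are. The downside is a less favourable stated joint power or, under the alternative, narrower claims.
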